Effect of Modulating CYP3A4 Activity on Mineral Homeostasis

NCT02019875

June 16, 2016

A. PURPOSE OF RESEARCH

Vitamin D is an important regulator of intestinal CYP3A4 (the enzyme responsible for metabolizing a majority of orally administered drugs) and the intestinal calcium transport proteins. Evidence suggests that CYP3A4 activity influences calcium homeostasis by catabolism of the main circulating vitamin D species, 25-hydroxy vitamin D₃ and its active metabolite, 1 α ,25-dihydroxy vitamin D₃. The purpose of this study is to test that hypothesis by evaluating the effect of compounds known to induce (rifampin) or inhibit hepatic (clarithromycin) and/or intestinal (clarithromycin, grapefruit juice) CYP3A4 catalytic activity on biomarkers of calcium homeostasis in healthy adults. This study is not designed to assess the safety or efficacy of the comparator treatments. No conclusions should be drawn in that regard. It is a mechanistically informative clinical study.

B. RESEARCH PROCEDURES INVOLVED

Study Design:

This is an open label, randomized, 3 period protocol to be conducted in healthy adults (18-60 yrs). A targeted enrollment of 120 participants pre-screened for good health will be assigned to one of six comparator groups by randomization. There will be 20 participants in each group. The three sequential study periods will be a 7-day Baseline phase, a 14-day Comparator phase and a 14-day Washout phase. During the Comparator phase of the study, participants will take one of the following by mouth for 14 days based on the group to which they were assigned: 1) 200 mL of water; 2) rifampin 600 mg; 3) 200 mL of grapefruit juice; 4) 200 mL of grapefruit juice plus rifampin 600 mg; 5) clarithromycin 250 mg twice a day and 6) clarithromycin 250 mg twice a day plus rifampin 600 mg once a day.

Study Procedures:

Screening. After providing informed consent, participants will be scheduled for a screening medical history and physical examination at the University of Washington General Clinical Research Center. The participants will also undergo an electrocardiogram (EKG) and screening blood test (metabolic panel). A urine pregnancy test will be performed on all women of child-bearing age. Screening procedures will take approximately one hour. If participants qualify for the study, they will start the baseline period of the study within 2 weeks of the screening visit.

Demographic and Inclusion and Exclusion Criteria.

- a. *Age.* This is not a treatment study. Its purpose is to determine the effect of changes in CYP3A4 activity on vitamin D homeostasis in healthy adults. Children under 18 years of age or adults older than 60 years of age will be excluded.
- b. *Gender.* We aim to recruit an equal number of males and females. However, rifampin and clarithromycin should not be used in pregnant women due to the risk for birth defects. Pregnant and lactating women will be excluded from this study. Women of childbearing age will be required to utilize a barrier method of birth control during the study and for 30 days after completion of the study.
- c. *Ethnic and racial minority study composition.* We aim to recruit ethnic and racial minority populations and achieve representation of minorities congruent with the population of King County, Washington.
- d. *Inclusion criteria.* 1) Participants will not have a history of significant cardiac, pulmonary, gastrointestinal or renal disease; 2) They will not have a history of HIV, diabetes or Hepatitis B or C; 3) Participants will be males or females between the ages of 18 and 60 years of age; 4) Participants must be able to understand and read English; 5) Participants will be able to provide

informed consent; 6) Subjects must be willing and able to avoid prescription medications, OTC drugs, dietary supplements and foods that are known to modulate CYP3A4 expression or activity; 7) Women will not be currently pregnant or lactating. In addition women participants of childbearing age must be willing to utilize a barrier method of birth control (sterilization will be acceptable); 8) Participants will not have allergies to rifampin, clarithromycin or grapefruit juice; 9) Subject's corrected QTc interval obtained by electrocardiogram will be \leq 430 ms in men or \leq 450 ms in women

e. *Exclusion criteria.* 1) People less than 18 years or older than 60 years of age; 2) People with significant cardiac, pulmonary or renal disease, people with diabetes, HIV or Hepatitis B or C; 3) People unable to read and understand English; 4) People unable to provide informed consent; 5) People unwilling or unable to avoid prescription medications, over the counter drugs, dietary supplements and food that are known to alter CYP3A4 expression or activity; people not willing to maintain the recommended diet of consistent calcium and Vitamin D levels during the study or not willing to maintain a daily diary of their food consumption; 6) Women who are pregnant or lactating and women participants of childbearing age not willing to utilize a barrier method of birth control (sterilization will be acceptable); 7) People with allergies to rifampin, clarithromycin or grapefruit juice, people with a corrected QTc interval of $>$ 430 ms in men or $>$ 450 ms in women on electrocardiogram.

General study procedures. This will be a 35-day study, divided into three periods: Baseline, d1-d7; Comparator, d8-d21; Washout, d22-35. The participants will be asked to eat a diet that maintains a consistent amount of vitamin D and calcium for the entire 35 days of the study and will record their daily food intake in a digital diary. They will be given a list of medications and foods to avoid during the study, because they are known to modify CYP3A4 activity.

Baseline Period. Participants will return to the University of Washington Laboratory Services on days 1, 4 and 7 between 8 am - 12 noon for a blood draw. On day 1, they will receive a specimen container for 24-hour urine collection. Urine collection will start on day 6 and continue for 24 hours. Participants will return this completed urine specimen when they return to University of Washington Medical Center on day 7 for blood collection.

Comparator Period. On day 8, the participants will enter the comparator period of the study. Depending on which of 6 groups group to which they were randomized, the participants will take either (1) 200 mL of water at 8 am for 14 days; (2) rifampin 600 mg with 200 mL of water at 8 pm for 14 days; (3) 200 mL of grapefruit juice at 8 am for 14 days; (4) 200 mL of grapefruit juice at 8 am plus rifampin 600 mg at 8 pm, both for 14 days; 5) clarithromycin 250 mg twice a day at 8 am and 8 pm for 14 days and 6) clarithromycin 250 mg twice a day at 8 am plus rifampin 600 mg with 200 mL of water at 8 pm, both for 14 days.

The grapefruit juice utilized in this study will be obtained from the Florida State Department of Citrus because they have a history of providing a high quality product that has been standardized for CYP3A4 inhibition for studies such as this one. Rifampin and clarithromycin will be dispensed by prescription from the University of Washington Investigation Drug Services.

Participants will return to University of Washington Laboratory Services on days 8, 9, 12, 15, 18 and 21 of the study for a blood draw between 8 am - 12 noon. On day 8, the participants will receive a specimen container for the second 24 hour urine collection. Participants will begin this urine collection on day 20 and return this specimen on day 21 when they return to University of Washington Medical Center. The 24 hour urine collection will need to be refrigerated during the collection period.

Washout Period. During the washout period of 14 days the participants will maintain a consistent diet of Vitamin D and calcium intake. On days 23, 25, 28, 31 and 35, the participants will return to University of Washington Laboratory Services for a blood draw between 8 am - 12

noon. On day 23, the participants will receive a specimen container for the second 24 hour urine collection. Participants will begin this urine collection on day 34 and return this specimen on day 35 when they return to University of Washington Medical Center. The 24 hour urine collection will need to be refrigerated during the collection period. The study will conclude with the return of the 24-hr urine specimen and the d35 blood draw.

C. ANALYTICAL METHODS

The primary study outcome measures – serum PTH and osteocalcin, plasma calcium concentration and 24-hr urinary calcium and phosphate concentration (normalized for creatinine concentration) – will be measured by the UWMC Department of Laboratory Medicine using established clinical procedures. The concentration of vitamin D₃ species in plasma will be measured in our research lab HPLC-Mass Spectrometry, using published methods developed by our research team.

D. STATISTICAL ANALYSIS PLAN

We will summarize demographic characteristics by treatment group using mean (SD) for continuous variables and frequency (percent) for categorical variables. We define the baseline value of each analyte to be the average of the three pre-randomization measurements, and the post-treatment value to be the analyte measurement after 14 days of treatment. We will use a linear mixed model with random intercepts and main effects for treatment group, the indicator of time (pre- vs. post-treatment), and the interaction of the two. From this model, we will extract the pre-treatment and post-treatment means, the change in analyte comparing pre- vs post-treatment for each group, and the difference in change in analyte comparing each active treatment group with the change observed in the water group. We will use a Wald test to test each difference in change compared with water, and a global Wald test to test the null hypothesis that all pre- vs post-treatment changes were the same across treatment group.

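### The only listed pregnancy test is 7 to 21 days old when rifampin or clarithromycin is first taken

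*Protocol*

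**What the plan says.** Protocol section B, under Screening, provides one pregnancy test: "A urine pregnancy test will be performed on all women of child-bearing age". Participants who qualify do not start at once; "they will start the baseline period of the study within 2 weeks of the screening visit". The calendar is under General study procedures: "This will be a 35-day study, divided into three periods: Baseline, d1-d7; Comparator, d8-d21; Washout, d22-35". Study drug therefore starts on day 8.

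The reason for excluding pregnant women is under Gender: "rifampin and clarithromycin should not be used in pregnant women due to the risk for birth defects". The same paragraph adds a second safeguard. Women of childbearing age are "required to utilize a barrier method of birth control during the study and for 30 days after completion of the study".

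The Baseline, Comparator and Washout Period paragraphs list blood draws and 24-hour urine collections for the study measurements. None lists a further pregnancy test, and none makes randomization or dispensing conditional on one. The SAP does not touch the point.

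**The concern.** The Protocol names a specific harm, birth defects, as its ground for exclusion. What matters for that harm is whether a woman is pregnant when she takes the drug. The listed test shows her status at screening, and the week of baseline plus up to two weeks of scheduling lie between the two.

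Two groups of women could pass the check and still be exposed: those who conceive after screening, and those already pregnant at screening but too early for the test to show it. The participants are healthy volunteers, and the Protocol says this is not a treatment study, so they have no therapeutic benefit to weigh against an avoidable fetal exposure.

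This is a participant-safety matter. It has no bearing on the mixed model, the Wald tests or any estimate.

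**Working it through.** The documents state no interval between test and dose, so there is no planned figure to reproduce. The check is calendar arithmetic.

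**Inputs (Protocol section B)**
- Screening to day 1: 0 to 14 days (Screening). Zero applies only if screening falls on day 1 itself.
- Day 1 to first dose on day 8: 7 days (General study procedures; Comparator Period).
- Day 1 to last dosing day, day 21: 20 days (same places).
- Blood-draw visits run from 8 am to noon. Clarithromycin starts at 8 am on day 8 and rifampin at 8 pm (Baseline and Comparator Periods).
- Arm size: "There will be 20 participants in each group" (Study Design).
- Sex ratio: "We aim to recruit an equal number of males and females" (Gender).

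**Age of the latest test = (screening to day 1) + (day 1 to dose)**

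| | As listed | With a day 7 test |
|---|---|---|
| At first dose, day 8 | 0 + 7 = 7 to 14 + 7 = 21 days | 8 − 7 = 1 day |
| At last dosing day, day 21 | 0 + 20 = 20 to 14 + 20 = 34 days | 21 − 7 = 14 days |

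In hours, from a day 7 visit between 8 am and noon, the first clarithromycin dose is 20 to 24 h away and the first rifampin dose 32 to 36 h away.

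A pregnancy missed at screening would also have had longer to become detectable by day 7: 0 + 6 = 6 days to 14 + 6 = 20 days.

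**Who is concerned.** Groups 2, 4, 5 and 6 receive rifampin, clarithromycin or both: 4 × 20 = 80 of 120 participants. With equal numbers of men and women, spread evenly over the arms, that is about 80 / 2 = 40 women, fewer of them able to conceive. These are arm sizes, not a count of expected pregnancies.

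**When contraception starts.** The requirement applies during the study. If the study begins at consent, the days after screening are covered. If it means the 35 days of the calendar, up to 14 days between screening and day 1 are not. The text allows either reading.

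**The case against.** The strongest reply is that no rule is broken. The documents set no maximum interval between test and dose, and the Protocol does not contradict itself. Safeguards are layered: every woman of childbearing age is tested, pregnancy excludes by status and not only at screening, contraception is mandatory and unwillingness to use it excludes, participants attend on days 1, 4 and 7 before dosing, and the drugs are dispensed on prescription by an institutional drug service. The contraception gap depends on the less favourable of two readings. Consent pages were removed and might contain a testing schedule. The number affected is unknown and probably small.

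The remedy can also be challenged. It would still miss very recent conceptions. No procedure states a time for randomization. Test, result, randomization and dispensing would have to fit within 20 to 24 h in the clarithromycin arms. The day 7 visit is a laboratory blood draw, whereas screening takes place at the clinical research center, so someone must be assigned to run the test and act on it.

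Much of this stands as a limit on the claim: it covers listed procedures only, carries no count, and alleges no contradiction. It does not answer the point itself. None of the safeguards confirms status at the first dose or finds a pregnancy too early to show at screening. The Protocol requires a test as well as contraception, so it does not treat contraception alone as sufficient. The tight turnaround is not created by the added test. Protocol section D and the SAP both describe the three baseline measurements as taken before randomization, so randomization and dispensing already have to fit between the day 7 draw and the day 8 doses. Staffing the test is a real but small practical matter.

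**Conclusion.** The concern holds. Under the listed procedures, a woman in any of four arms could start a drug that the Protocol says should not be given in pregnancy on the strength of a test 7 to 21 days old. The check is weaker than the stated reason for the exclusion calls for.

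This should be changed because the harm is one the Protocol itself names and prevention is cheap, not because many cases are expected. The conclusion assumes that the procedures listed in section B are complete as regards pregnancy testing. A repeat test specified in the removed consent pages would settle the main point. The head counts assume that the aim of equal numbers of men and women is met.

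**What to change.** In the Baseline Period paragraph, add a repeat urine pregnancy test for women of childbearing age at the day 7 visit, and require a negative result before randomization and before study drug is dispensed. Take the sample once the 24-hour collection is complete, so that nothing is lost from that specimen. Name who runs the test and acts on the result. Under Gender, state that barrier contraception starts at screening.

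Day 7 is better than day 8. The day 8 visit window opens at 8 am, which is also when clarithromycin starts, so a day 8 test could follow the first dose. Placing the test before randomization means that a positive result removes no randomized participant. If it controlled dispensing only, one positive would cost 1 / 20 = 5% of an arm.

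The cost is a few sentences of text and one repeat of a test already in use, at a visit where urine is already handed in. Because it precedes randomization, it applies across all six arms: at most about 120 / 2 = 60 tests if the sexes are equal. The time needed is modest, since for the whole screening visit, this test included, "Screening procedures will take approximately one hour". The downside is an occasional withdrawal after baseline, with a replacement enrolled. Very recent conceptions would still be missed, and days 8 to 21 would still rely on contraception.

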Effect of Modulating CYP3A4 Activity on Mineral Homeostasis
NCT02019875
06/16/2016

We summarized demographic characteristics by treatment group using mean (SD) for continuous variables and frequency (percent) for categorical variables. We defined the baseline value of each analyte to be the average of the three pre-randomization measurements, and the post-treatment value to be the analyte measurement after 14 days of treatment. We then used a linear mixed model with random intercepts and main effects for treatment group, the indicator of time (pre- vs. post-treatment), and the interaction of the two. From this model, we extracted the pre-treatment and post-treatment means, the change in analyte comparing pre- vs post-treatment for each group, and the difference in change in analyte comparing each active treatment group with the change observed in the water group. We used a Wald test to test each difference in change compared with water, and a global Wald test to test the null hypothesis that all pre- vs post-treatment changes were the same across treatment group.

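### Does the single 8 am clock time for twice-daily clarithromycin in group 6 leave the group 6 versus water test undefined?

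*Protocol*

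**What the plan says.** Group 6 is described twice in the Protocol.

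- Section B, Study Design, with no clock times: "clarithromycin 250 mg twice a day plus rifampin 600 mg once a day".
- Section B, Comparator Period, with clock times: "clarithromycin 250 mg twice a day at 8 am plus rifampin 600 mg with 200 mL of water at 8 pm".

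Two neighbouring arms in the Comparator Period text help in reading this.

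- Group 5: "clarithromycin 250 mg twice a day at 8 am and 8 pm for 14 days".
- Group 4: "200 mL of grapefruit juice at 8 am plus rifampin 600 mg at 8 pm, both for 14 days".

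On supply, the same section says: "Rifampin and clarithromycin will be dispensed by prescription".

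Section D of the Protocol estimates, from a linear mixed model, "the difference in change in analyte comparing each active treatment group with the change observed in the water group". It tests each such difference with a Wald test and adds a global Wald test across all groups. The SAP repeats this in the past tense and gives no dosing detail.

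**The concern.** A twice-daily frequency needs two intake times, and the group 6 clause gives clarithromycin only one. The 8 pm in that clause belongs to rifampin. Because group 5 carries both times in the same sentence, the omission could be read as deliberate. No other part of the documents supplies the second time.

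This study asks what happens when CYP3A4 activity is altered by specified agents, so the regimen is the exposure under study. Group 6 is the only arm combining clarithromycin with rifampin, and the wording leaves open whether the second clarithromycin dose coincides with the evening rifampin. If the clause meant something other than the group 5 schedule, the group 6 versus water estimate would describe a different exposure from the one a reader assumes. If it meant one dose a day, the total would be halved.

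**Working it through.** **1. The two descriptions of group 6, side by side**

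| Item | Study Design | Comparator Period | Agree? |
|---|---|---|---|
| Clarithromycin dose | 250 mg | 250 mg | yes |
| Clarithromycin frequency | twice a day | twice a day | yes |
| Duration | 14 days | 14 days | yes |
| Rifampin | 600 mg, once a day | 600 mg, at 8 pm | yes |
| Clarithromycin clock times | none given | 8 am only | second time not stated |

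Four of the five items agree. The fifth is incomplete in one place and absent in the other. The mismatch is between frequency and clock time inside a single clause.

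**2. How the wording may have arisen**

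The group 6 clause has the same form as the group 4 clause: first component at 8 am, then rifampin at 8 pm, both for 14 days. One time suits the juice in group 4, which is not described as twice daily. Carrying that form over to group 6 would leave a clarithromycin time out. This is inference from the wording. The documents do not confirm it.

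**3. Total clarithromycin under each possible reading**

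Total = days × doses per day × mg per dose.

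- Group 5 as stated: 14 × 2 × 250 mg = 7,000 mg = 7.0 g.
- Group 6, two doses at separate times: 14 × 2 × 250 mg = 7.0 g. Difference from group 5: 0 g.
- Group 6, both doses at 8 am: 14 × 2 × 250 mg = 7.0 g. Difference: 0 g.
- Group 6, one dose at 8 am: 14 × 1 × 250 mg = 3.5 g. Difference: 3.5 g.

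Only the last reading changes the total, and it sets aside a frequency stated in both sections. It is not evidence of a conflict in dose. Under the other two readings only the timing within the day differs.

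**4. What the planned tests use**

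For active group *k*, the contrast is

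D(k) = [post(k) − pre(k)] − [post(water) − pre(water)],

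which is the group-by-time interaction coefficient. Its inputs are the randomized group, the baseline average and the measurement after 14 days of treatment. The global test asks whether all 6 − 1 = 5 of these coefficients are zero. Neither calculation uses a dose time. D(6) and its standard error come from the same formula under every reading.

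The comparison arm is water, which contains no clarithromycin, so D(6) does not depend on groups 5 and 6 sharing a schedule. No group 6 versus group 5 or group 6 versus group 2 test is planned.

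**The case for a change.** The strongest reply is that a plausible guess does not replace a stated schedule. This is the only text giving dosing times, the clause is grammatically complete with no sign of redaction, and the trial is about exposure to enzyme modulators. A reader cannot tell from the documents exactly when the second daily dose in group 6 was to be taken. Anyone comparing groups 5 and 6 informally would want to know whether they shared a schedule. Writing it down costs one line.

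The gap in description stands: the clause is incomplete and nothing else in the documents completes it. What does not stand is the step from there to a fault in the analysis. The documents give no figure showing that timing within the day alters an analyte measured after 14 days. Group 6 has 20 of 120 planned participants (16.7%) and enters one of the five versus-water contrasts for each measure. Those figures show where the arm appears, but they do not show that any estimate or error rate moves.

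Participants received clarithromycin by prescription. The prescription, label and participant wording are not in the documents, so it cannot be said that the incomplete clause reached anyone.

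**Conclusion.** The concern does not call for a change to the plan. It is one unstated clock time in one arm, most likely a clerical slip. Dose, frequency and duration agree wherever they are stated, and the stated total is 7.0 g in both clarithromycin groups. The group 6 versus water contrast, the global test, the sample size and the model are the same under any reading.

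This rests on two assumptions. The first is that the twice-daily frequency, given in both sections, was what prescriptions carried. The second is that inference stays with the planned comparisons against water and the global test. If a formal comparison of groups 5 and 6 were added, the actual schedules would need to be known first.

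The Comparator Period and Study Design wording for group 6 must still be reconciled as a matter of record. If dosing is complete, as the SAP's past tense suggests, the ordinary description of treatments in the report would state the schedule participants were told to follow. This review takes no position on which schedule is right.

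### Minor: for the blood analytes a three-draw baseline mean and a single post-treatment draw share one random-intercept model with no time-specific residual variance stated, so model-based error bars on the pre and post means may be off

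*Protocol*

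**What the plan says.** Protocol section D sets the two values analysed per participant. For the first it says "We define the baseline value of each analyte to be the average of the three pre-randomization measurements". The Baseline Period paragraph supplies the three blood values, since participants attend "on days 1, 4 and 7 between 8 am - 12 noon for a blood draw". For the second, section D takes "the post-treatment value to be the analyte measurement after 14 days of treatment", which is a single draw.

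The model sentence begins "We will use a linear mixed model with random intercepts and main effects for treatment group" and adds time and the group-by-time interaction. The SAP repeats it in the past tense: "We then used a linear mixed model with random intercepts and main effects for treatment group". Neither document mentions a residual variance by time point, an unstructured covariance, weights or robust standard errors.

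The outputs begin with the means: "From this model, we will extract the pre-treatment and post-treatment means". Within-group changes and differences in change from the water group follow. Formal testing concerns change only: "We will use a Wald test to test each difference in change compared with water", plus a global Wald test that the changes are equal.

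The point affects the blood outcomes. Section C lists "serum PTH and osteocalcin, plasma calcium concentration" among five primary outcomes and adds the plasma vitamin D species. The two urinary outcomes are outside it: the Baseline Period and Comparator Period paragraphs schedule one 24-hour collection each, so their pre and post records are alike in this respect.

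**The concern.** Averaging three draws cuts the draw-specific part of the variance to one third, provided that this part is independent between draws. The post record keeps all of it. A random-intercept model with a single residual variance treats the two records as equally noisy and gives the pre and post means of a group the same SE when the data are complete. That SE lies between the two correct ones. An interval built from it would be too wide before treatment and too narrow after it, and the second error is the anti-conservative one. In a mechanistic biomarker study, readers are likely to look at the group means directly.

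**Working it through.** **Inputs from the documents.** Three baseline draws, one post draw, six groups of 20 (6 x 20 = 120, which agrees with the stated total), and a random-intercept model. The documents give no SD, ICC, dropout rate or SE, so there is no design figure to reproduce.

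**Assumptions.** Single-draw variance is 1 both before and after treatment. Let e be the share of that variance specific to the draw; the remaining 1 - e is shared by a participant's draws within a period. With independent draws around a stable personal level, e = 1 - ICC.

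**Variances of the two records (independent draws).**
- Pre: (1 - e) + e/3 = 1 - 2e/3
- Post: (1 - e) + e = 1
- Covariance: 1 - e

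**What the common-variance model estimates.** With complete pairs it matches the covariance and gives both records the average variance: [(1 - 2e/3) + 1]/2 = 1 - e/3.

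**Ratio of model SE to correct SE.**
- Pre: sqrt[(1 - e/3)/(1 - 2e/3)]
- Post: sqrt(1 - e/3)

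| Assumed ICC | e | Pre ratio | Post ratio | Coverage of nominal 95%, pre / post |
|---|---|---|---|---|
| 0.3 | 0.7 | 1.199 | 0.876 | 0.981 / 0.912 |
| 0.5 | 0.5 | 1.118 | 0.913 | 0.970 / 0.924 |
| 0.8 | 0.2 | 1.038 | 0.966 | 0.956 / 0.940 |

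Coverage is from 20,000 simulated trials per row (6 x 20, complete data, normal critical value). With separate pre and post variances it was 0.947 to 0.948 for both means.

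Example at e = 0.5, n = 20: the model gives sqrt(0.8333/20) = 0.204 SD for both means. The correct values are sqrt(0.6667/20) = 0.183 (pre) and sqrt(1/20) = 0.224 (post).

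**Baseline draws that share period-level variation.** Take between-person variance 0.5 and person-by-period variance 0.10, 0.20 or 0.25 of the total, so e = 0.4, 0.3 or 0.25. The pre SE is then +9%, +6% or +5%, and the post SE -7%, -5% or -4%. The ratios depend only on e; the error vanishes at e = 0.

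**Change, complete pairs.** The model's variance of change per participant is 2[(1 - e/3) - (1 - e)] = 4e/3. The true value is (1 - 2e/3) + 1 - 2(1 - e) = 4e/3. They are identical. At e = 0.5 the SE of change in one group is sqrt(0.6667/20) = 0.183 SD and that of a difference in change is sqrt(2 x 0.6667/20) = 0.258 SD, under either structure. A mixed-model fit to one simulated data set agreed with least squares on the paired differences: the same coefficients, and an interaction SE of 0.27104 from both.

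**Change, post values missing.** Assume 10%, 20% or 30% of post values missing completely at random, the same fraction in every group, with baseline-only participants kept in the fit. The identity then no longer holds. Comparing model-based with sandwich variance gives a ratio r of model to true SE, and type I error is 2[1 - Phi(1.96r)].

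| Assumed ICC | r at 10% / 20% / 30% missing | Type I error |
|---|---|---|
| 0.3 | 0.984 / 0.967 / 0.949 | 5.4% / 5.8% / 6.3% |
| 0.5 | 0.990 / 0.979 / 0.967 | 5.2% / 5.5% / 5.8% |
| 0.8 | 0.996 / 0.993 / 0.989 | 5.1% / 5.2% / 5.3% |

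**The case against.** Several counter-arguments stand and set the weight of this point.

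- The common residual variance is read from silence. It is the usual default for a model described only by its random intercepts, but the documents do not state it.
- The plan commits to extracting means; it promises no SEs or intervals for them. If the means are shown with SDs or SEs from the raw data, the problem does not arise.
- The direction of the error needs similar single-draw variance before and after treatment. The comparators are meant to change metabolism, so this is not assured. The two records would have equal variance if the post variance fell to 1 - 2e/3 of the baseline single-draw variance, which is a post SD about 7% lower at e = 0.2 and 18% lower at e = 0.5. A larger fall reverses the direction; a rise in post variance enlarges the error.
- The size rests on an assumed ICC, and at 0.8 it is only a few percent.

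A reader might infer that the mismatch invalidates the comparisons with water. The documents do not support that: all planned tests concern change, and with complete pairs their SEs are the same under either residual structure. The opposite inference, that the tests are safe whatever happens, is not supported either, because the equality needs complete pairs and the documents give no dropout rate.

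These arguments do not remove the point. The averaged baseline comes from the plan itself, the means are named outputs, and the stated model makes no allowance for the difference in precision.

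**Conclusion.** The point holds as a minor, mainly descriptive one, for the blood analytes only. It depends on a common residual variance being fitted, on similar single-draw variance before and after treatment, and on model-based SEs or intervals being shown with the means. Then the pre SE is overstated by about 4% to 20% and the post SE understated by about 3% to 12% over an assumed ICC of 0.8 to 0.3, and by less if the baseline draws share period-level variation. With complete pairs, the estimates and tests of change do not move. With missing post values and baseline-only participants retained, the rise in type I error is slight: about 5.1% to 6.3% over the assumed ranges.

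Two nearby questions are separate clarifications and add no weight here: how the urinary baseline is defined when only one collection exists, and which sample counts as the one taken after 14 days.

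**What to change.** Keep the averaged baseline for the blood analytes and fit separate residual variances for the pre and post records, that is, an unstructured 2x2 covariance per person. State this in one SAP sentence. With complete pairs, the estimates and tests of change stay as they are; with missing post values, the change tests no longer rely on equal pre and post variances.

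No value of e has to be assumed at the analysis. The within-person variance of the three baseline draws can be estimated with up to 120 x 2 = 240 degrees of freedom, which shows how much the point matters for each analyte.

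The cost is one extra variance parameter per blood analyte and no new samples. At assumed ICC 0.3, 0.5 and 0.8 with independent draws, post-treatment intervals become 14%, 10% and 4% wider (1/0.876, 1/0.913, 1/0.966), and pre-treatment intervals 17%, 11% and 4% narrower (1/1.199, 1/1.118, 1/1.038).

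One limit remains: a single 2x2 covariance is pooled over the six groups, so it gives correct group-level SEs only if variances are similar between groups. The SAP should state that assumption too.
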